1.2 Synopsis

Name of Sponsor: AbbVie	Protocol Number: S187.3.005
Name of Finished Product: Levodopa-Carbidopa Intestinal Gel (LCIG) 20 mg/mL - 5 mg/mL	Phase of Development: 3
Name of Active Ingredient: Levodopa-Carbidopa	Date of Protocol Synopsis: 17 December 2013
Protocol Title: Open-Label Continuation Treatment Study with Levodopa-Carbidopa Intestinal Gel in Subjects with Advanced Parkinson's Disease and Severe Motor-Fluctuations Who Have Exhibited a Persistent and Positive Effect to Treatment in Previous Studies	
Study Center(s) (Planned): Approximately 70	
Study Duration: The protocol duration is planned until the finished product is available commercially in the respective countries where subjects are participating in the study. The expected protocol duration will continue through successful NDA and subsequent approval (approximately 4 years). The protocol duration will be extended 4 years in the UK from the approval date of Amendment 3.01. If it is deemed necessary to continue treatment after 4 years in the UK, either an amendment will be made to the current protocol or a new protocol will be submitted.	
Objectives: The primary objective is to provide continued access to subjects who would like to continue Levodopa-Carbidopa Intestinal Gel (LCIG), after completion of an open-label study (S187.3.003 or S187.3.004). The secondary objectives are to assess the long-term safety and tolerability of the LCIG therapeutic system, and to assess the maintenance of efficacy using data collected from US subjects.	
Methodology: This is a Phase 3B, open-label, multi-center, study. Subjects will be provided with LCIG, if judged medically indicated and if it is not commercially available. Data collected will be for evaluation of safety and efficacy, and for periodic assessment of the continued appropriateness of the subject's participation in the study. The decision to continue is based on the Principal Investigator's clinical judgment.	
Number of Subjects (Planned): It is anticipated that approximately 275 subjects who had participated and completed one of the open-label LCIG clinical trials will be eligible for this continued treatment with LCIG, until it is commercially available.	

Diagnosis and Main Criteria for Inclusion:

In order to be eligible to participate in this study, subjects must meet the following criteria:

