12.1.4 Adverse Events of Special Interest

Adverse events of special interest (AESI) for LCIG are:

- Risks of PEG-J insertion
- Long-term complications of PEG-J
- Device associated gastrointestinal disorders during long-term therapy

- Cardiovascular fatalities
- Aspiration including aspiration pneumonia
- A diagnosis of peripheral polyneuropathy; axonal, demyelinating or mixed type
- Possible symptoms of peripheral polyneuropathy such as sensory disturbances or loss of strength, which from their course and clinical presentation or from their response to medication could be precursors of polyneuropathy
- Clinically significant weight loss

A standard panel of examinations will be suggested to the Investigators if one of the study subjects develops signs and symptoms of polyneuropathy. The panel should be considered as a basic recommendation and the selection of additional diagnostic tools is at the discretion of the Investigator, depending on the clinical presentation of the individual subject.

For AESIs, serious and nonserious, meeting pre-defined criteria, specific questionnaires will be used to standardize the collection of follow-up information.

All cases of clinically significant weight loss and possible symptoms or precursors of polyneuropathy (serious and non serious) should be reported on the Report for SAEs and AESIs (Yellow Form) to the Sponsor (or an authorized representative) within the expedited timelines applicable for SAEs.

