13.2 Analysis Populations

Definitions of analysis populations:

1. Safety Population:
The Safety Population includes all subjects who have taken at least one dose of study medication in this study. The Safety Population will be used for all analyses unless noted otherwise.
2. Efficacy Population:
The Efficacy Population includes all subjects who have taken at least one dose of study medication in this study and have at least one efficacy assessment in this study.

This is an open-label study with a single, active treatment group; all subjects in this study will receive LCIG.

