For a missing/incomplete stop date the maximum of the following will be imputed:

- The minimum of the latest possible stop date and the date of last administration of investigational study drug
- The earliest possible stop date
- The earliest possible start date

Here, the earliest (latest) possible date is defined as:

- The date itself if it is possible
- The date of the first (last) day of the month, if month and year are available but the day is missing
- The date of the first (last) day of the year, if year is available but day and month are missing
- A very early (late) date, for example, 01JAN1000 (01JAN3000), if the date is completely missing

From this data the following will be determined and used for presentation in the applicable tables and listings:

- Treatment-Emergent Adverse Events (TEAEs): Defined as AEs which started on or after the Date of the First 3005 LCIG Infusion and within 30 days of the Date of the Last 3005 PEG-J Exposure.
- Treatment-Emergent Serious Adverse Events (TESAEs): Defined as TEAEs regarded by the Investigator as Serious.
- TEAEs that are at least possibly related to the therapeutic system: Defined as TEAEs assessed as having a "Possible" or "Probable" relationship to the investigational therapeutic system and includes those events where the relationship is missing.
- Severe TEAEs: Defined as TEAEs assessed as being "Severe" in intensity and includes those events where the severity is missing.
- TEAEs that led to premature discontinuation: Selected as those events where: "Led to Study Termination" is indicated as "Yes."
- TEAEs with fatal outcome as reported on the "Adverse events" CRF.
- TEAEs in the following categories have been defined as TEAEs of special interest:
 - Procedure and device associated events
 - Polyneuropathy (broad search as well as narrow search)
 - Weight loss

- Cardiovascular fatalities
- Respiratory tract aspiration including aspiration pneumonia/pneumonitis

TEAEs are included in a category of special interest based on their PT and, in the case of cardiovascular fatalities, their outcome. The list of PT's assigned to each category is included as Appendix 12.4. Only TEAEs where an outcome of "Fatal" has been reported on the "Adverse Event" CRF are to be included in the category of cardiovascular fatalities. All events with PT's other than those assigned to the procedure and device associated AESI category will be included in summaries of events that are not procedure and device related.

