10014431	Electromyogram abnormal	
10017062	Formication	
10017577	Gait disturbance	
10068912	Genital hypoaesthesia	
10020937	Hypoaesthesia	
10021089	Hyporeflexia	
10021118	Hypotonia	
10027910	Mononeuritis	
10062203	Mononeuropathy	
10027918	Mononeuropathy multiplex	
10061296	Motor dysfunction	
10028289	Muscle atrophy	
10028372	Muscular weakness	
10056677	Nerve degeneration	
10062284	Neuromuscular toxicity	
10029323	Neuromyopathy	
10029332	Neuropathy vitamin B6 deficiency	
10029350	Neurotoxicity	
10033775	Paraesthesia	
10067633	Peripheral nerve lesion	
10058530	Peripheral nerve palsy	
10071663	Peripheral nerve paresis	

Code	Preferred Term	Narrow Search (N)
10034699	Peroneal muscular atrophy	
10034701	Peroneal nerve palsy	
10064964	Phrenic nerve paralysis	
10054786	Skin burning sensation	
10068015	Temperature perception test decreased	
10052492	Tinel's sign	
10045380	Ulnar neuritis	

3. Weight loss (CMQ 80000109).

Code	Preferred Term
10000159	Abnormal loss of weight
10002647	Anorexia and bulimia syndrome
10002649	Anorexia nervosa
10060961	Appetite disorder
10005895	Body mass index decreased
10006895	Cachexia
10061428	Decreased appetite
10012775	Diet refusal
10013950	Dysphagia
10014062	Eating disorder
10061832	Eating disorder symptom
10050366	Fear of eating
10053050	Gastrointestinal tube insertion
10052592	Gastrostomy tube insertion
10063743	Hypophagia
10021577	Inadequate diet
10061273	Malnutrition
10026820	Marasmus
10028155	Multi-vitamin deficiency
10065026	Nutritional condition abnormal
10029861	Nutritional support
10051284	Parenteral nutrition

Code	Preferred Term
10050086	Poor weight gain neonatal
10041954	Starvation
10048828	Underweight
10056814	Weight abnormal
10047894	Weight decrease neonatal
10047895	Weight decreased
10049040	Weight fluctuation
10047897	Weight gain poor
10047901	Weight loss diet

4. Cardiovascular fatalities: major adverse cardiovascular events (MACE) MI CMQ (80000076) and the outcome of the AE was fatal.

Code	Preferred Term
10051592	Acute coronary syndrome
10000891	Acute myocardial infarction
10054015	Agonal rhythm
10002388	Angina unstable
10003225	Arteriospasm coronary
10005468	Blood creatine phosphokinase abnormal
10005470	Blood creatine phosphokinase increased
10005472	Blood creatine phosphokinase MB abnormal
10005474	Blood creatine phosphokinase MB increased
10007515	Cardiac arrest
10049993	Cardiac death
10007548	Cardiac enzymes increased
10007617	Cardio-respiratory arrest
10007625	Cardiogenic shock

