10063078	Bronchoalveolar lavage abnormal
10006469	Bronchopneumonia
10053582	Bronchopneumopathy
10053420	Bronchopulmonary disease
10006479	Bronchoscopy
10006480	Bronchoscopy abnormal
10008589	Choking
10008590	Choking sensation
10057482	Dependence on respirator
10060865	Duodenogastric reflux
10013950	Dysphagia
10013968	Dyspnoea
10013969	Dyspnoea at rest
10013971	Dyspnoea exertional
10067450	Endotracheal intubation
10063349	Endotracheal intubation complication
10052591	Enteral nutrition
10015894	Extubation
10056661	Feeding tube complication
10016985	Forced expiratory volume abnormal
10016987	Forced expiratory volume decreased
10017000	Foreign body aspiration
10017505	Functional residual capacity abnormal
10017508	Functional residual capacity increased
10053050	Gastrointestinal tube insertion
10064069	Gastrointestinal tube removal
10017885	Gastrooesophageal reflux disease
10052592	Gastrostomy tube insertion
10020591	Hypercapnia

Code	Preferred Term
10020910	Hyperventilation
10020952	Hypocapnia
10021079	Hypopnoea
10021133	Hypoventilation
10021143	Hypoxia
10062530	Increased bronchial secretion
10062717	Increased upper airway secretion
10061257	Jaw disorder
10024378	Leukocytosis
10024738	Lobar pneumonia
10057260	Lower respiratory tract inflammation
10025080	Lung consolidation
10025082	Lung disorder
10025102	Lung infiltration
10026882	Mastication disorder
10049783	Mendelson's syndrome
10056652	Middle lobe syndrome
10058525	Nasal aspiration
10059841	Nasopharyngeal reflux
10049235	Nocturnal dyspnoea
10061877	Obstructive airways disorder
10056992	Oesophagobronchial fistula
10067472	Organising pneumonia
10031123	Orthopnoea
10058982	PCO2 abnormal
10034181	PCO2 decreased
10034193	Peak expiratory flow rate abnormal
10034195	Peak expiratory flow rate decreased
10067353	Pharyngeal disorder
10070912	Pharyngeal dyskinesia
10035664	Pneumonia
10035669	Pneumonia aspiration
10060946	Pneumonia bacterial

Code	Preferred Term
10035730	Pneumonia primary atypical
10035742	Pneumonitis
10035745	Pneumonitis chemical
10062087	PO2 abnormal
10035768	PO2 decreased
10059184	Poor dental condition
10066590	Post procedural pneumonia
10036790	Productive cough
10037368	Pulmonary congestion
10037660	Pyrexia
10053307	Radiography guided aspiration
10067869	Reflux laryngitis
10062102	Removal of foreign body
10038330	Removal of foreign body from larynx
10038333	Removal of foreign body from oesophagus
10059390	Removal of foreign body from respiratory tract
10038334	Removal of foreign body from throat

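### The aspiration and weight-loss AESI totals rest on broad term lists with no narrow counterpart, so they are sensitive but not specific to the two protocol risks

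*SAP*

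**What the plan says.** Protocol 12.1.4 names the two risks as "Aspiration including aspiration pneumonia" and "Clinically significant weight loss".

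SAP 8.5.1 sets the rule for membership: "TEAEs are included in a category of special interest based on their PT and, in the case of cardiovascular fatalities, their outcome". The PTs are printed in SAP 12.4, item 3 (weight loss, CMQ 80000109) and item 5 (respiratory tract aspiration, CMQ 80000103). Each percentage is the number of subjects with at least one event of the type, divided by the Safety sample.

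Both lists contain "Gastrointestinal tube insertion", "Gastrostomy tube insertion" and Dysphagia.

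Only polyneuropathy is given both a broad and a narrow search (SAP 8.5.1; Tables 14.3__1.2.2.12 and 14.3__1.2.2.13). SAP 10.1 records the merging of three procedure and device categories as a change from the protocol. It does not mention these two lists.

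**The concern.** The protocol describes two specific clinical events, while the SAP counts anyone with any term from a wide screening list. A subject whose only listed event is a fever, raised white cells or breathlessness enters the aspiration total. A subject whose only listed event is a swallowing symptom enters both totals.

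The protocol's statistical objective is long-term safety, and "This is an open-label study with a single, active treatment group". With no control arm to carry the same background of non-specific terms, the absolute percentage is the result that will be read. A table titled as aspiration-related or weight-loss-related invites the reader to take its total as the incidence of that risk.

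**Working it through.** No figure in the plan depends on this point, so there is nothing to reproduce. The check is a count of the printed lists, their overlap, and an illustration on assumed rates.

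**1. Counts (SAP 12.4)**

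| | Aspiration, item 5 | Weight loss, item 3 |
|---|---|---|
| Distinct PTs | 130 | 31 |
| PTs naming the target | 8 contain the word aspiration | 10 name weight or BMI |
| Pyrexia | yes | no |
| Dysphagia | yes | yes |
| Gastrointestinal tube insertion | yes | yes |
| Gastrostomy tube insertion | yes | yes |
| Gastrointestinal tube removal | yes | no |
| Feeding tube complication | yes | no |

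- Aspiration: 8/130 = 6%. One of the 8, Radiography guided aspiration, reads as a procedure. Dropping it and adding Mendelson's syndrome and Pneumonitis chemical gives 8 − 1 + 2 = 9 PTs, or 9/130 = 7%.
- Weight loss: 10/31 = 32%. The 10 include two neonatal terms and Weight loss diet.

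**2. Cross-counting**

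- The two lists share three PTs: Dysphagia and the two insertion terms.
- Dysphagia is also in the broad polyneuropathy list, so one such event counts in three categories.
- Gastrointestinal tube insertion is also in the procedure and device list (item 1), so it too counts in three.
- Gastrostomy tube insertion is not in item 1. SAP 8.5.1 sends every PT outside item 1 to the summaries of events that are not procedure and device related. This term would therefore count as aspiration, as weight loss, and as not procedure or device related.

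**3. Why the PT rows do not give the narrow count**

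AET006 counts subjects within each PT. A subject with both Aspiration and Pneumonia aspiration appears in two rows. If n_i is the count in row i of a narrow set, the number of distinct subjects N_narrow satisfies only

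max(n_i) ≤ N_narrow ≤ Σ n_i.

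The exact value would have to be rebuilt from listing AEL006, with the terms chosen after the data are seen.

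**4. Illustration (all rates assumed; none is in the documents)**

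Take independent subject-level rates: true aspiration 2% to 6%, Pyrexia 2% to 10%, Dysphagia 2% to 8%, tube terms 0% to 5%. The category rate is 1 − Π(1 − p_i), and the planned number is "approximately 275 subjects who had participated".

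- Low: 1 − 0.98 × 0.98 × 0.98 = 5.9%, about 16 of 275.
- High: 1 − 0.94 × 0.90 × 0.92 × 0.95 = 26.1%, about 72 of 275.
- High with tube terms at 0%: 1 − 0.94 × 0.90 × 0.92 = 22.2%.
- Lowest share of counted subjects with true aspiration: 0.02 / (1 − 0.98 × 0.90 × 0.92 × 0.95) = 0.02/0.229 = 9%.
- Highest share: 0.06 / (1 − 0.94 × 0.98 × 0.98) = 0.06/0.097 = 62%.

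The share of true events runs from 9% to 62% according to what is assumed. The illustration shows that the over-count does not need the tube terms, but it does not estimate its size.

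**The case against.** **The specific events are visible.** AET006 breaks each category down by SOC and PT, AEL006 lists the events, and AET002 and AET003 show all TEAEs by PT. The AET001 overview carries no AESI line. A reader might infer that the totals fail to measure aspiration or weight loss at all, or that true aspiration is hidden. The documents do not support that: the target events are included and have their own rows. What remains is the missing unduplicated narrow count.

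**Weight is measured directly.** SAP 8.5.3 has a potentially clinically significant criterion of at least a 7% decrease from Baseline. Weight is summarized over time (Table 14.3__5.1.11), and the criterion is reported overall and by visit (Tables 14.3__5.2.1 and 14.3__5.2.2). This softens the weight-loss half considerably, although it does not make the AESI total specific. No comparable measured outcome is planned for aspiration.

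**Tube changes are not automatically adverse events.** Because every subject has a PEG-J, a reader might infer that tube replacements will swell both totals. SAP 6.4.3 puts the initial placement in Study 3001, 3002 or 3004, before this study, and SAP 8.5.5.2 records placements and removals on the Device Information eCRF. A tube change reaches these lists only if an investigator reports it as an adverse event and it codes to one of the tube terms. The documents do not show that this is common.

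**Breadth suits safety screening.** A sensitive list is a defensible choice, and the two CMQs are printed without the narrow flag that the polyneuropathy SMQs carry. A narrow list also loses aspiration coded as Pneumonia or Choking. This argues for reporting both counts rather than replacing one with the other.

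**Conclusion.** The point holds as one of specificity. The four table totals capture the protocol's events together with an unknown number of subjects who had only a non-specific listed term. This rests on the printed lists and the PT rule, and needs no assumption.

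The size of the over-count cannot be stated from the documents. A reader might want to attach a multiple to it, but any multiple depends on PT rates that are not given and on independence. Independence is doubtful, because fever or breathlessness can accompany aspiration and some true aspiration may be coded as Pneumonia. It would also be wrong to infer that fever counts as weight loss, since Pyrexia is in the aspiration list only.

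The placement of Gastrostomy tube insertion is a separate classification inconsistency that needs resolving however often the term occurs. Overall this is an inexpensive improvement to the reporting and does not invalidate the safety analysis.

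**What to change.** 1. Label the current aspiration and weight-loss totals as broad search.
2. Add to SAP 12.4 a pre-specified narrow search for each category, with a unique-subject count shown beside the broad one. The final terms are for the sponsor's medical review. Candidates are:
   - Aspiration: Aspiration, Aspiration bronchial, Aspiration tracheal, Aspiration tracheal abnormal, Foreign body aspiration, Nasal aspiration, Pneumonia aspiration, Mendelson's syndrome, Pneumonitis chemical.
   - Weight loss: Abnormal loss of weight, Weight decreased, Body mass index decreased, Cachexia, Underweight.
3. State that the weight-loss AESI is to be read beside the existing 7% criterion.
4. Keep the tube-procedure terms in the broad tables but report them separately there.
5. Reconcile Gastrostomy tube insertion with the procedure and device list.
6. Record the broad and narrow definitions in SAP 10.1.

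The cost is appendix wording and a few extra AET006 tables, with no change to data collection. The narrow search can miss poorly coded events, but these stay visible in the broad table.
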